
Inclusion Criteria
	
 1. Meet the diagnostic criteria for refractory rheumatoid arthritis 2. Patients who have been treated with conventional disease-modifying rheumatic drugs and have been treated with 2 or more biologic/targeted disease-modifying anti-rheumatic drugs and require Abciap in combination with JAK inhibitors

Exclusion Criteria
	
 1. Those who do not meet the above inclusion criteria 2. Patients with tumors, hematological diseases and other autoimmune diseases 3. History of allergy to the drugs selected for this study 4. Patients who cannot adhere to the treatment of Abciap combined with JAK inhibitors, or who have serious adverse reactions and have not completed the observation course specified in the study

Research Progress Plan
	
2022.03-2024.03

Statistical analysis methods
	
SPSS software was used for statistical analysis. Normality tests were performed using SPSS software was used for statistical analysis. Normality tests

	
were performed using the Kolmogorov-Smirnov test, and measures conforming to a normal distribution were expressed as mean \pm standard deviation ($\bar{x} \pm s$), and comparisons between groups were made using the two independent samples t-test; measures not conforming to a normal distribution were described by median and interquartile spacing, i.e., median (25th percentile, 75th percentile) [M(P25,P75)], and comparisons between groups were made using the Mann-Whitney U anecdotal test The difference between groups was considered statistically significant at $P < 0.05$. The data were analyzed by the chi-square test or Fisher's exact probability method.

Form of publication of research results	Published 1-2 papers

1. Purpose of the study

(1) To observe the effect of Abasip combined with JAK inhibitor on the clinical efficacy of D2TRA patients

(2) To observe the safety of Abciap combined with JAK inhibitor in the treatment of D2TRA patients

2. Background of the study

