Sei Muraoka et al. Abatacept is Efficacious in the Treatment of Older Patients with csDMARD-Refractory Rheumatoid Arthritis: A Prospective, Multicenter, Observational Study. This Japanese prospective, multicenter, observational study demonstrated that abciap is effective and safe in older RA patients with a history of csDMARDs-refractory disease. In both younger and older patients with csDMARDs-refractory RA, abciap was shown to be more effective than adding or switching to new csDMARDs.

Sae Ochi et al. Preferable outcome of Janus kinase inhibitors for a group of difficult-to-treat rheumatoid arthritis patients: from the FIRST Registry. This Japanese study compared the response to different classes of b/tsDMARDs in D2TRA and vD2TRA patients who were not responding to multiple b/tsDMARDs. The results suggest that JAK inhibitors are the preferred treatment option for this type of D2TRA.

(2) Subject selection basis

Patients diagnosed with refractory rheumatoid arthritis who meet the 2021 European League Against Rheumatism (EULAR) diagnostic criteria for refractory rheumatoid arthritis

4. Research Content

(1) Test population: patients with refractory rheumatoid arthritis

(2) Sample size: 90 D2TRA patients

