No intervention factors were imposed on the study subjects in the study. Prospectively, 90 patients with D2TRA who were ineffective to conventional disease-modifying antirheumatic drugs and ineffective to treatment with 2 or more biological/targeted disease-modifying antirheumatic drugs and treated with Abacap combined with JAK inhibitors attending the outpatient and inpatient departments of Zhejiang Provincial People's Hospital from March 2022 to March 2024 were included as the observation group. Thirty patients with D2TRA treated with abciap alone in the outpatient and inpatient departments of Zhejiang Provincial People's Hospital from August 2020 to November 2021 were selected as the historical control group. There was no statistically significant difference between the observation group and the control group in terms of gender, age, disease duration, number of pressure pain in 28 joints, number of swelling in 28 joints, and DAS28 score ($P > 0.05$). The dosage was 125 mg per dose by subcutaneous injection once a week, and the dosage was 5 mg per dose by oral injection twice a day. The drug was billed according to the maximum number of days of medical insurance (4 weeks), and patients were observed for rheumatoid factor, anti-cyclic citrullinated peptide antibodies, immunoglobulins (IgG, IgA and IgM), C-reactive protein, blood sedimentation, white blood cells, platelets, ghrelin, glutamic aminotransferase, glutamic oxalacetic aminotransferase, globulin, creatinine, glomerular filtration rate, 28 joints at 4, 8, 12, 16, 20 and 24 weeks before and after drug administration number of pressure pain, number of swelling in 28 joints, joint ultrasound, change in DAS28-ESR score and adverse effects. To observe the changes in laboratory test indices, number of pressure pain in 28 joints, number of swelling in 28 joints, and DAS28 scores in the Abciap combined with JAK inhibitor treatment group, before and after self-comparison at 0, 4, 8, 12, 16, 20, and 24 weeks, as well as the changes in joint ultrasound and adverse effects. Also retrospectively collected the changes in laboratory test indices, number of pressure pain in 28 joints, number of swelling in 28 joints, and DAS28 score in the group treated with Abacap alone, and performed a before-and-after self-comparison at 0, 4, 8, 12, 16, 20, and 24 weeks, while observing the changes in joint ultrasound and adverse effects. In addition, we observed the changes in laboratory indices, the number of pressure pain in 28 joints, the number of swelling in 28 joints, and the DAS28 score between the Abciap and JAK inhibitor treatment groups at 0, 4, 8, 12, 16, 20, and 24 weeks, and compared them between the two groups. The changes in joint ultrasound and adverse effects between the two groups were also observed, so as to observe the clinical efficacy and safety of the Abciap combined with JAK inhibitor treatment group. $DAS28 \leq 2.6$ was defined as clinical remission, $2.6 < DAS28 \leq 3.2$ as low activity, $3.2 < DAS28 \leq 5.1$ as moderate activity, and $DAS28 > 5.1$ as high activity.

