including the Declaration of Helsinki ethical guidelines for human medical research and the relevant Chinese clinical research study norms and regulations. In the course of the study, if there is a need to revise this protocol, the revised protocol must be submitted to the Ethics Committee again for approval before implementation.

The Informed Consent Form for this study has been approved by the Medical Ethics Committee. If the Informed Consent Form is amended in writing, it will be sent to the Ethics Committee for approval to obtain the subject's consent again. Before the start of the study, the investigator provides patients with detailed information about the study, including the nature of the study, the purpose of the study, the possible benefits and risks, and the rights and obligations of the patients. The patient is fully informed and agrees, and signs the Informed Consent Form before the study can begin.

11. Statistical analysis plan

SPSS software was used for statistical analysis. Normality tests were performed using the Kolmogorov-Smirnov test, and measures conforming to a normal distribution were expressed as mean \pm standard deviation ($\bar{x} \pm s$), and comparisons between groups were made using the two independent samples t-test; measures not conforming to a normal distribution were described by median and interquartile spacing, i.e., median (25th percentile, 75th percentile) [M(P25,P75)], and comparisons between groups were made using the Mann-Whitney U anecdotal test Comparisons between groups were made using the Mann-Whitney U anecdotal sum test; count data were expressed as percentages, and comparisons between groups were analyzed using the chi-square test or Fisher's exact probability method, with differences considered statistically significant at $P < 0.05$.

12、 Form of publication of research results

Published 1-2 papers

13.Data Logging Form

Observed indicators		Week 0	Week 4	Week 8	Week 12	Week 16	Week 20	Week 24
Rheumatoid factor	IU/ml							
Anti-cyclic citrulli	U/ml							

nated peptide antibody								
Immunoglobulin G	g/L							
Immunoglobulin A	g/L							
Immunoglobulin M	g/L							
C-reactive protein	mg/L							
Blood sedimentation	mm/h							
Leukocytes	$\times 10^9/L$							
Blood platelets	$\times 10^9/L$							
Glutathione aminotransferase	U/L							
Glutathione transa	U/L							

minase								
Globulin	g/L							
Creatinine	umol/L							
Glomerular filtration rate	ml/min							

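### The only analysis stated for safety laboratory values compares means or medians, so it does not show how many patients had marked abnormalities

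*Protocol*

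**What the plan says.** Safety is the second of two objectives in section 1: "To observe the safety of Abciap combined with JAK inhibitor in the treatment of D2TRA patients". Section 7 lists what is observed at each visit, including white cells, platelets, immunoglobulins and "glutamic aminotransferase, glutamic oxalacetic aminotransferase, globulin, creatinine, glomerular filtration rate". The section 13 form records these as plain values at weeks 0, 4, 8, 12, 16, 20 and 24.

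The Program Summary, section 4(3) and section 7 treat laboratory indices like joint counts and DAS28: change within each group at each visit, then a comparison between groups. The Program Summary and section 4(3) judge that comparison at P < 0.05.

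Section 11, which is headed as the statistical analysis plan, gives one rule for all measured values. If normal, "measures conforming to a normal distribution were expressed as mean" and SD, with a two-sample t-test. If not, "measures not conforming to a normal distribution were described by median and interquartile spacing", with Mann-Whitney. For counts, "count data were expressed as percentages, and comparisons between groups were analyzed using the chi-square test or Fisher's exact probability method". No text turns a laboratory reading into a count of patients.

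The observation group is 90 patients ("Sample size: 90 D2TRA patients") and the historical control group is 30.

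**The concern.** For these variables the safety question lies in the tail: how many patients crossed a limit, and how far. The stated summaries describe the centre of the group. A drug effect that raises liver enzymes sharply in a few percent of patients leaves the median almost where it was, and a rank test counts each such patient only as one high rank, however extreme the value.

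The stake is a table of medians with non-significant P values that contains no sign of several patients with marked toxicity, in a study where safety is half of the stated purpose.

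**Working it through.** The protocol gives no laboratory limit, SD, event rate or power, so there is no figure of its own to reproduce. What follows is an illustration.

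**Inputs from the protocol:** 90 combination patients, 30 controls, significance at 0.05 (taken as two-sided).

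**Assumptions:** an enzyme value at one visit, log-normal with median 20 U/L and log SD 0.4 in both groups, except that k of the 90 combination patients have 150 U/L.

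**Shift of the median by formula.** With k = 5, the median of 90 sits at the 45/85 quantile of the 85 unaffected values: 20 × exp(0.4 × z), where z = Φ⁻¹(45/85) = 0.074. This gives 20.6 U/L, a shift of 0.6 U/L.

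**Simulation, 20,000 trials per row:**

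| k of 90 | Median | P75 | Mann-Whitney rejects | Pooled t rejects | Welch t rejects |
|---|---|---|---|---|---|
| 0 | 20.0 | 26.1 | 5.1% | 5.2% | 5.2% |
| 2 | 20.3 | 26.7 | 4.9% | 0.3% | 9.9% |
| 5 | 20.6 | 27.7 | 6.5% | 1.2% | 49.7% |
| 9 | 21.2 | 29.3 | 10.6% | 19.6% | 96.9% |

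Shorter runs of the same set-up gave 10% to 12% for Mann-Whitney at k = 9. Up to five affected patients, Mann-Whitney stays close to its false-positive rate.

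**Other assumed values.** With median 22 U/L, the same log SD and affected patients at 200 to 400 U/L (3,000 runs), Mann-Whitney rejects in 5.6%, 5.0%, 6.3% and 9.9% for k = 2, 3, 5 and 9. The conclusion about the rank test does not depend on the size of the extreme values.

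**Which branch of section 11 applies.** Under the first set of assumptions with k = 5, a Kolmogorov-Smirnov test with Lilliefors correction rejected normality of the combination group in all of 500 runs. The protocol's own rule then leads to the median and Mann-Whitney.

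**What counting would show** (Clopper-Pearson 95% CI; Fisher against 0/30):

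- 2/90 = 2.2% (0.3% to 7.8%), p = 1.00
- 5/90 = 5.6% (1.8% to 12.5%), p = 0.33
- 9/90 = 10.0% (4.7% to 18.1%), p = 0.11

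The chance of seeing at least one case among 90 is 1 − (1 − p)⁹⁰: 60% at a true rate of 1%, 84% at 2%, 94% at 3% and 99% at 5%.

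**Whether the adverse event route fills the gap.** Section 9(2) limits reporting to events related to the study drug. Its severity scale rests on symptoms and function; the scale under the section 14 form rests on treatment and discontinuation. Neither contains a laboratory limit, and no text requires an abnormal value to be entered as an event. A marked value that led to no treatment and no discontinuation would be mild on the section 14 scale, if entered at all.

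**The case against.** The strongest reply is that laboratory summaries are one strand of safety. Adverse effects are compared between groups, the section 14 form records severity, relationship, outcome and withdrawal for each event, and the count-data rule can be applied to them. That form also has boxes for events judged unrelated, so the related-only rule of section 9(2) does not close every route. A steep enzyme rise on treatment might well be judged possibly related and reported. This stands. A reader might infer that the safety objective goes unanswered; the documents do not support that.

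A second reply is that section 11 is generic. It names no laboratory test, its count-data rule does not forbid abnormality counts, and section 9 mentions individual data analysis and scatter plots. Shift tables are also often left to a separate analysis plan, which may exist. This lowers the weight of the point. It does not remove it: section 9 gives no method, and the comparison that is stated for laboratory indices is of measured values.

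A third inference to resist is that skewness sends these variables to the least responsive test. That depends on the version of the t-test, which section 11 does not name. With five affected patients the pooled version rejects less often than Mann-Whitney (1.2% against 6.5%), the Welch version far more often (about 50%).

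Finally, the fix will not make the between-group comparison conclusive, as the Fisher values show. That is correct.

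**Conclusion.** The point holds in a limited form. The analysis stated for safety laboratory values does not show how many patients had marked abnormalities, and the adverse event data cover this only in part. The laboratory part of the safety objective is poorly served.

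The size rests on assumed values. For 2 to 5 affected patients of 90, the rank test is close to its false-positive rate under both sets of assumptions tried; at 9 of 90 it detects the difference in about one trial in ten. Whether a future report would present such a result as good safety cannot be known from the protocol.

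Two other provisions could hide the same patients. Exclusion criterion 4 removes those with serious adverse reactions who did not complete observation. The data-cleaning step in section 9 allows upper and lower limits for outliers without stating them, although it is aimed at implausible values.

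**What to change.** Add to section 11, for each safety laboratory value:

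- a shift table of week 0 against the worst value after week 0, classified by the laboratory's reference limits;
- the number and percentage of patients beyond the limit and beyond multiples of it fixed in advance, by group, with exact 95% CI.

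Include every treated patient with any value after week 0, and reconcile this with exclusion criterion 4. State that verified extreme values are neither removed nor capped. Keep means and medians as description, and state that a non-significant test is not evidence of safety.

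The readings are already on the section 13 form. The cost is recording the reference limits, which the form lacks, and one table per variable. No additional patients or visits are needed.

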
8. Start and end of the experiment

9.Data Security and Monitoring Program

(This paragraph cannot be deleted, if not, fill in none. According to the requirements of the Ministry of Health's Measures for Ethical Review of Biomedical Research Involving Human Beings (2016), all research projects are required to have a data security and monitoring plan, and this item is one of the criteria for the ethics committee to review the project, please describe it specifically according to the requirements.)

(1) Overview of data management methods

1.Data are traceable. All clinical trial data correspond to specific subjects and investigators, and all modifications to the data are recorded in detail to create a series of traceable verification traces.

2.Correctness of data. The correctness of data mainly includes the authenticity and accuracy of data, all clinical trial data reflect the actual situation of the study truthfully without any falsification, fiction and tampering; the accuracy is reflected in the verifiable data sources, i.e. CRF, study records and entered data should be consistent with the data obtained from the actual study.

3.Data completeness. Study data were collected completely for each subject, and missing data due to special reasons were stated as to why they were missing.

4.Logical reasonableness of the data. To determine whether the data are logically unreasonable from a clinical perspective.

5.Timeliness of data. The data are observed and completed in a timely manner at the specified time points in the clinical trial.

(2) Adverse events and serious adverse events are reported and collected.

Reporting principles: 1. Report only adverse events related to the study drug 2. Complete the Spontaneous Adverse Event Report Form for all related adverse events (serious and non-serious)

The following information should also be included to determine if the event is related, possibly related, or potentially related to the drug. Determination of event-drug relevance includes: 1. reasonable temporal sequence 2. dose-response relationship 3. pharmacology 4. discontinuation of dosing and/or positive re-dosing.

Classification of the severity of drug-related adverse events:

Mild	The symptoms do not alter the patient's normal function.
Moderate	The symptoms result in some degree of functional impairment, but are not damaging, uncomfortable, or embarrassing.
Severe	The symptoms are definitely detrimental to health, with significant

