Glomerular filtration rate	pcs							
Swollen number of 28 joints	pcs							
DAS28-ESR score	score							
Ultrasound of joints								

14. Adverse reaction record form

No adverse events have occurred	 yes  no
Name of undesirable events	
Start date of occurrence	____ Year ____ month ____ day
Dosing time and dosage	____ year ____ month ____ day ____ mg
Severity*	 Mild  Moderate  Severe
Whether to take	 yes  no

measures	
Relationship to study drugs	 Definitely related  Likely related  Possibly related  Possibly unrelated  Definitely not related
Outcome of adverse events that occurred	 Still exists  Eased  No idea Relief Date _____ year _____ month _____ day
Whether the patient withdrew from the trial because of the adverse event	 yes  no

Severity*: mild (no treatment, no discontinuation), moderate (discontinuation, no treatment), severe (discontinuation, control treatment)

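### The section 14 adverse reaction form records dosing, causality and measures once for a two-drug regimen and offers no fatal outcome, so the section 9(2) causality criteria can be applied only in part and only to the combination as a whole

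*Protocol*

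**What the plan says.** Section 7 describes an observation group of 90 patients "treated with Abacap combined with JAK inhibitors" and a historical control group: "Thirty patients with D2TRA treated with abciap alone". It gives two dosing statements without naming the drug in either: "The dosage was 125 mg per dose by subcutaneous injection once a week, and the dosage was 5 mg per dose", the second being oral and twice daily.

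Section 9(2) asks for a judgement of whether an event is related to the drug, in the singular, on these grounds: "reasonable temporal sequence 2. dose-response relationship 3. pharmacology 4. discontinuation of dosing and/or positive re-dosing". It restricts reporting to related events and requires a Spontaneous Adverse Event Report Form for all of them, serious or not. The contents of that form are not shown.

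The section 14 form has:
- an onset date;
- one line for "Dosing time and dosage", with one date, one mg blank and no drug name;
- a severity grade, whose footnote ties the grade to whether treatment was discontinued;
- a yes/no item on measures;
- one five-level item, "Relationship to study drugs", which includes two unrelated levels;
- "Outcome of adverse events that occurred", with three choices (still present, eased, not known) and a relief date;
- a yes/no item on withdrawal of the patient from the trial because of the event.

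**The concern.** Safety of the combination is one of the two stated purposes in section 1. Three of the four causality criteria (timing, dose-response, and stopping or re-dosing) need to know which drug is meant once two are taken together. Take a patient with raised transaminases who stops one drug and continues the other. The form shows neither which drug was stopped, nor when, nor whether it was restarted.

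The outcome list is closed. Whoever completes the form after a death must tick a category that does not fit or leave the item blank.

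Causality also has a practical role in this protocol. It decides whether the separate report is made, and section 9 makes serious consequences directly related to the study one of the triggers for halting it.

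**Working it through.** No arithmetic applies. The check sets the form against the regimen in section 7 and the four criteria in section 9(2).

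**Regimen against form.** The combination group has two drugs and two schedules. The form has one dosing date, one dose blank, one causality item and one yes/no item on measures. The amount entered (125 or 5 mg) might hint at which drug is meant, but that is an inference and not a recorded drug identity. For the abatacept-alone controls, the single fields are enough to identify the drug.

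**Criterion by criterion, on this form:**

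| Section 9(2) criterion | What section 14 holds | Result |
|---|---|---|
| Timing | Onset date and one dosing date, drug not named | Partly supported, for the regimen as a whole |
| Dose-response | One mg entry | Not supported per drug |
| Pharmacology | Needs no field | Can be applied |
| Stopping and/or re-dosing | Discontinuation implied by the severity footnote; relief date; patient-level withdrawal item. No stop date, no re-dosing field, no drug named | Stopping only roughly inferable for the regimen; re-dosing not recorded |

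The tally is one criterion applicable, two partly supported for the regimen as a whole, and one not supported per drug.

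**How far the severity grade shows discontinuation.** The section 14 footnote defines moderate and severe by discontinuation. Section 9(2) defines the same three grades by functional impairment. A moderate grade therefore need not mean that a drug was stopped, and it never says which one.

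**Outcome list.** There are three choices, none of them fatal and none for recovery with sequelae.

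**Which events reach the other form.** The Spontaneous Adverse Event Report Form is required for related events only. Section 14 also takes events judged unrelated. For those, the section 14 form is the only dedicated adverse event record that the protocol shows. A death judged unrelated therefore has no valid outcome entry on section 14 and does not trigger the other form.

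**Other records.** The section 13 data log has no row for drug exposure. The case collection form in section 9 lists treatment in general terms and might hold some dosing data, but its layout is not shown.

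**The case against.** The strongest reply is that section 14 is not the whole safety record. Section 9(2) requires a separate report for every related event and, on its face, attaches the causality information to that report. Its contents are unknown, and the case collection form may hold treatment dates. This stands as far as it goes: it cannot be concluded that per-drug dosing or death is captured nowhere. It does not reach events judged unrelated, and nothing shown says that the separate form works per drug.

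A second reply is that the planned safety comparison is between groups. The added effect of the JAK inhibitor comes from that contrast, and counting events by the regimen started is an accepted convention. This also stands. The between-group count needs no per-drug attribution; the loss lies in interpreting it and in knowing exposure at onset.

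Three stronger readings are tempting, and the document does not support them:

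- A reader might infer that the section 9(2) criteria cannot be applied at all. The criterion table shows otherwise.
- A reader might infer that every combination-group event is compromised. An event with no change in treatment loses no information on stopping or re-dosing.
- A reader might infer that a countable number of patients who drop one drug will have later events charged to the combination. The protocol gives no rate of single-drug stopping. Exclusion criterion 4 also appears to remove patients who cannot adhere to the combination, and those with serious reactions who do not complete the course. Whether such removal is sound is a separate question.

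**Conclusion.** The point holds as a defect of the section 14 form. For the two-drug group, the form cannot show which drug was given, suspected, stopped or restarted. The section 9(2) criteria can therefore be applied from it only in part, and only to the combination as a whole. A death has no valid outcome entry.

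The number of events affected cannot be stated from the protocol. It depends on how many of the 90 patients change one drug after an event, and on how many die. The conclusion assumes that the form is completed as printed and that the two dosing statements in section 7 refer to abatacept and the JAK inhibitor. It makes no assumption about the content of the Spontaneous Adverse Event Report Form. If that form proves to be per drug and to include death, the gap narrows to events judged unrelated. The point does not bear on the efficacy comparison.

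**What to change.** Revise section 14 as follows:

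1. Split the rows for last dose (date and amount), relationship and action taken into one column for abatacept and one for the JAK inhibitor. Record action as continued, interrupted, stopped or restarted, with dates.
2. Add recovered with sequelae and fatal to the outcome list.
3. Reconcile the form with section 9(2) and with the Spontaneous Adverse Event Report Form. State which form holds the causality information, and align the two definitions of the severity grades so that discontinuation is read from its own field.
4. As a supplement to the whole-group count, tabulate combination-group events by the drugs being taken at onset. This table can be specified in the statistical analysis plan.

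These changes concern data capture and alter no treatment. The cost is a slightly longer form, one extra table, and completion from the chart for events already recorded.
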